14.2.2 Source data verification

Source data verification ensures accuracy and credibility of the data obtained. During monitoring visits, reported data are reviewed with regard to being accurate, complete, and verifiable from source documents (eg, subject files, recordings from automated instruments, tracings [ECG], X-ray films, laboratory notes). All data reported on the eCRF should be supported by source documents, unless otherwise specified in Section 14.2.1.

14.3 Data handling

14.3.1 Case Report Form completion

The study will use electronic data capture (EDC); the Investigator will be responsible for prompt reporting of accurate, complete, and legible data in the eCRFs and in all required reports.

Any change or correction to the eCRF after saving must be accompanied by a reason for the change.

Corrections made after the Investigator's review and approval (by means of a password/electronic signature) will be reapproved by the Investigator.

The Investigator should maintain a list of personnel authorized to enter data into the electronic eCRF. Access to the EDC will be given after training has been received. A training certificate will be provided and filed.

Serious AE reporting will be done using the SAE Report Form (see Section 12.1.2.3) while also entering the event in the appropriate eCRF section. The safety database and the clinical database will be reconciled during the study and discrepancies will be corrected as needed.

Detailed instructions will be provided in the eCRF Completion Guidelines.

14.3.2 Database entry and reconciliation

Case Report forms/external electronic data will be entered/loaded into a validated electronic database using a clinical data management system (CDMS). Computerized data cleaning checks will be used in addition to manual review to check for discrepancies and to ensure consistency of the data. The data will be entered into the eCRFs once and will be subsequently verified if the study is performed using electronic data capture.

An electronic audit trail system will be maintained within the CDMS to track all data changes in the database once the data have been saved initially into the system or electronically loaded. Regular backups of the electronic data will be performed.

14.3.3 Subject Screening and Enrollment log/Subject Identification Code list

The subject's screening and enrollment will be recorded in the Subject Screening and Enrollment log.

The Investigator will keep a Subject Identification Code list. This list remains with the Investigator and is used for unambiguous identification of each subject.

The subject's consent and enrollment in the study must be recorded in the subject's medical record. These data should identify the study and document the dates of the subject's participation.

14.4 Termination of the study

UCB reserves the right to temporarily suspend or prematurely discontinue this study either at a single site, multiple sites, or at all sites at any time for reasons including, but not limited to, safety or ethical issues, inaccurate or incomplete data recording, noncompliance, or unsatisfactory enrollment with respect to quality or quantity.

If the study is prematurely terminated or suspended, UCB (or its representative) will inform the Investigators/institutions and the regulatory authority(ies) of the termination or suspension and the reason(s) for the termination or suspension, in accordance with applicable regulatory requirement(s). The IRB/IEC should also be informed and provided with reason(s) for the termination or suspension by the sponsor or by the Investigator/institution, as specified by the applicable regulatory requirement(s). In addition, arrangements will be made for the return of all unused IMP and other material in accordance with UCB procedures for the study.

14.5 Archiving and data retention

The Investigator will maintain adequate records for the study, including eCRFs, medical records, laboratory results, Informed Consent documents, drug dispensing and disposition records, safety reports, information regarding participants who discontinued, and other pertinent data.

All essential documents are to be retained by the Investigator until at least 2 years after the last approval of a marketing application in an ICH region and until there are no pending or contemplated marketing applications in an ICH region, or at least 2 years have elapsed since the formal discontinuation of clinical development of the IMP. These documents should be retained for a longer period, however, if required by the applicable regulatory requirement(s) or by an agreement with UCB (CPMP/ICH/135/95, 2002 [Section 4.9.5]). The Investigator will contact UCB for authorization prior to the destruction of any study records or in the event of accidental loss or destruction of any study records. The Investigator will also notify UCB should he/she relocate or move the study-related files to a location other than that specified in the sponsor's trial master file.

14.6 Audit and inspection

The Investigator will permit study-related audits mandated by UCB, after reasonable notice, and inspections by domestic or foreign regulatory authorities.

The main purposes of an audit or inspection are to confirm that the rights and wellbeing of the subjects enrolled have been protected, that enrolled subjects (ie, signing consent and undergoing study procedures) are appropriate for the study, and that all data relevant for the evaluation of the IMP have been processed and reported in compliance with the planned arrangements, the protocol, investigational site, and IRB/IEC SOPs, ICH GCP, and applicable regulatory requirements.

The Investigator will provide direct access to all study documents, source records, and source data. If an inspection by a regulatory authority is announced, the Investigator will immediately inform UCB (or designee).

14.7 Good Clinical Practice

Noncompliance with the protocol, ICH-GCP, or local regulatory requirements by the Investigator, institution, institution staff, or designees of the sponsor will lead to prompt action by UCB to secure compliance. Continued noncompliance may result in the termination of the site's involvement in the study.

15 STATISTICS

A description of statistical methods follows and will be described in more detail in the SAP. Deviations from the original SAP will be documented in the clinical study report (CSR).

15.1 Definition of analysis sets

The Enrolled Set (ES) will consist of all subjects who have given informed consent.

The Randomized Set (RS) will consist of all randomized subjects.

The Safety Set (SS) will consist of all subjects who receive at least 1 dose of the IMP.

The Full Analysis Set (FAS) will consist of all randomized subjects who receive at least 1 dose of the IMP and have a valid measurement of the primary efficacy variable at Baseline and at least 1 post-baseline efficacy assessment.

The Per-Protocol Set (PPS) will consist of all subjects in the FAS who have no important protocol deviation affecting the primary efficacy variable. The subjects with important protocol deviations will be predefined and evaluated during a data evaluation meeting prior to unblinding of the data.

The Pharmacokinetics Per-Protocol Set (PK-PPS) will consist of all randomized subjects who receive at least 1 dose of the IMP and have at least 1 quantifiable post-dose plasma concentration.

The PET Per-Protocol Set (PET-PPS) will consist of all randomized subjects who receive at least 1 dose of the IMP and have evaluable PET-CT or PET-MRI scan data at Baseline and at least 1 of the post-Baseline assessments.

Further details of each analysis set along with specifications of analyses by analysis set will be provided in the SAP.

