5.3 Imaging evaluation

In a subpopulation of AS0013, a PET-MRI or PET-CT scan of the entire spine will be performed at selected sites in approximately 25 subjects at Screening, and during the study at Week 12 and Week 48/Early Withdrawal Visit if PET-positive lesions were observed in the previous scan.

The PET-MRI or PET-CT scan should be performed after confirmation of eligibility for the study based on screening assessments. All subjects at selected sites are eligible provided that a separate Informed Consent form (ICF) for the imaging evaluation has been signed.

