^o A PET-MRI or PET-CT scan should be done up to 2 weeks before Baseline and within 2 weeks after the W12 and W48/WD Visit if PET-positive lesions are observed in the previous scan. If a subject withdraws from the study early, the PET-MRI or PET-CT scan must be repeated at the WD visit only, if the prior examination was done more than 12 weeks prior to the WD visit and the previous PET-scan showed positive lesions.

^p CZP 400mg sc Q2W at Weeks 0, 2, and 4 (loading dose) followed by CZP 200mg sc Q2W in Weeks 6 to 10 and 400mg Q4W from Week 12 to Week 44. Bimekizumab will be administered at a dose of 160mg sc Q2W from Week 0 through Week 10 and 320mg sc Q4W from Week 12 to Week 44. The IMP will be administered at the end of the visit after all assessments have been completed. Subjects randomized to bimekizumab will receive 1 placebo injection at Baseline

[figure not shown]
Table 5–1: Schedule of assessments

Study Period	SCr	Treatment Period								Treatment Extension Period								SFU ^a
Visit ^b /Week (Visit window ± 3 days)	V1	V2	V3	V4	V5	V6	V7	V8	V9	V10	V11	V12	V13	V14	V15	V16	V17	V18
Procedures	SV	BL W0	W2	W4	W6	W8	W10	W12	W16	W20	W24	W28	W32	W36	W40	W44	W48 /WD	W64

(Visit 2), Week 2 (Visit 3), and Week 4 (Visit 4).

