### 3.5.8 PET Per-Protocol Set

The PET Per-Protocol Set (PET-PPS) will consist of all randomized subjects who receive at least 1 dose of the IMP and have evaluable PET-MRI or PET-CT scan data at Baseline and at least 1 of the post-Baseline assessments.

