Another reader who has not been involved in the visual identification of the PET-positive lesions, either as a primary reader or an adjudicator, will then draw volumes of interest (VOIs) on the pre-identified PET-positive lesions. In the case that no PET-positive lesions have been identified for a subject, then the final review step to draw VOIs will not occur. Efficacy PET-MRI/PET-CT review will occur provided that an acceptable PET-CT or PET-MRI scan is available and that PET-positive lesions were identified on the previous scan (for the Week 12 and Week 48 visits). During the PET-positive lesion VOI review, the independent reviewer will perform a quantitative assessment in ACCURATE and record the standard uptake values of  $^{18}\text{F}$ -fluoride in VOIs, corrected for both body weight and individual integrated whole blood activity concentration (SUVauc) for each PET-positive lesion identified during the PET-positive lesion identification review.

Data from the visual identification of PET-positive lesions and the results of the quantitative VOI review (i.e. SUVauc) will be listed, for each independent reader and adjudicator (if applicable), for each anatomical location in the spine, and for each side of the SIJ, by treatment group and visit for subjects in the SS who were enrolled into the PET-MRI/PET-CT substudy.

No formal statistical modelling of the PET-MRI/PET-CT imaging data will be performed for this substudy; only summaries will be presented together with 95% CIs for mean values, as applicable.

The summaries described below based on the visual identification of PET-positive lesions will include the final assessment data, ie, if adjudication was performed, then the adjudicated data will be summarized, otherwise data from one of the primary reviewers will be summarized.

All summaries will be presented for the PET-PPS.

Since the attenuation correction and quantification is variable in PET-MRI scans, PET-MRI imaging data will be listed but will not be aggregated with the PET-CT imaging data in the summaries.

Due to the predicted sparseness of the number of PET-positive lesions in each of the individual anatomical locations of the spine, data will be pooled as follows for the purpose of some of the summaries:

- In the SIJ and spine overall (across the SIJ and all anatomical locations in the spine);
- In the SIJ overall (across both sides), and split by Left and Right side;

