- In the spine overall (across all anatomical locations in the spine), and split by spinal regional level (Cervical, Thoracic, Lumbar, Sacrum), and, depending on the distribution of lesions across the spine, further by spinal levels and spinal locations in which at least 1 PET-positive lesion is identified.

An overview of the total number of PET-positive lesions identified in the spine across all subjects in each of the individual anatomical locations will be presented by visit.

The presence of PET-positive lesions identified in the SIJ and spine will be summarized by visit. The summary will include the number and percentage of subjects at each visit with any PET-positive lesions in the spine or the SIJ, in both the spine and the SIJ, in the SIJ overall (and split by Left and Right side) and in the spine overall [and split by spinal regional level (Cervical, Thoracic, Lumbar and Sacrum) and level/location, as applicable]. This summary will also

include a total count of PET-positive lesions across subjects for each of the pooled locations described above. In the spine, the incidence and the total number of lesions will only be presented for the anatomical locations in which at least 1 PET-positive lesion is identified.

The number of PET-positive lesions per subject in the SIJ and spine (overall and in pooled locations, as described above) will be calculated and summarized by visit using frequency counts and percentages, and/or descriptive statistics, as applicable. In addition, in the spine and SIJ overall, in the spine overall and in each spinal regional level, the changes in the number of PET-positive lesions per subject from Baseline to Week 12 and Week 48, and the changes from Week 12 to Week 48 will be summarized using descriptive statistics.

Bar charts summarizing the total number of PET-positive lesions identified in the SIJ and in the spine will be presented by treatment group and visit for each of the pooled locations described above.

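### Baseline PET lesion prevalence in the PET-PPS is 100% by construction, because only subjects PET-positive at Baseline can enter the set

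*Protocol*

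**What the plan says.** **Who is in the set.** Protocol 15.1 requires that subjects "have evaluable PET-CT or PET-MRI scan data at Baseline and at least 1 of the post-Baseline assessments". SAP 3.5.8 gives the same rule: subjects must "have evaluable PET-MRI or PET-CT scan data at Baseline and at least 1 of the post-Baseline assessments". SAP Table 3-1 takes the Screening scan as the PET Baseline.

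**When a later scan exists.** Protocol 5.3 schedules scans at "Week 12 and Week 48/Early Withdrawal Visit if PET-positive lesions were observed in the previous scan". At early withdrawal, the footnote to Protocol Table 5-1 asks for a repeat only "if the prior examination was done more than 12 weeks prior to the WD visit and the previous PET-scan showed positive lesions". SAP 8.3.6.2 places the same condition on the efficacy read, which needs an acceptable scan and also "that PET-positive lesions were identified on the previous scan (for the Week 12 and Week 48 visits".

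**What is tabulated on it.** SAP 8.3.6.2 states: "All summaries will be presented for the PET-PPS". The planned tables include "the number and percentage of subjects at each visit with any PET-positive lesions", the number of lesions per subject by visit, total lesion counts with bar charts, and changes in lesion number between visits. Under SAP 3.1, percentages use the analysis set and treatment group as denominator unless stated otherwise.

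**Who may join the substudy.** Protocol 5.3 asks only for a signed imaging consent at a selected site. The eligibility read in SAP 8.3.6.1 concerns the SIJ radiograph. A positive PET scan is not an entry condition, and SAP 8.3.6.2 provides for subjects in whom no lesion is found.

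**The concern.** Set membership depends on having a follow-up scan, and having a follow-up scan depends on the Baseline result. A Baseline prevalence row computed on that set tells the reader nothing about prevalence, but it will look like a finding: every subject had at least one active lesion. The zero category in the Baseline frequency table of lesions per subject can never be filled, and the Baseline mean is a mean among positives only.

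This matters because the imaging work is descriptive. The rationale for Protocol Amendment 3 says that the sponsor is still learning how these endpoints are distributed, and SAP 2.4 says that the aim is to identify which variables might differ between arms. How many subjects with active AS have a lesion at Baseline, and how many lesions each has, are the first facts such a study should supply. The same selection also touches the planned within-arm changes: a set chosen for a positive first read will tend to show somewhat fewer lesions at the second read even with no treatment effect.

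**Working it through.** The plan states no expected PET-positivity rate, lesion count or PET power, so there is no stated figure to reproduce. The first step is pure logic. The later steps use assumed values, marked as such.

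**1. Can a Baseline-negative subject qualify?** Let each of Baseline, Week 12 and Week 48/WD be positive or negative, and let each later scan be missed or not: 2^5 = 32 patterns. A later scan exists only if it was not missed and the last available scan was positive.

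- Baseline negative (16 patterns): no Week 12 scan and no Week 48 scan. None qualifies.
- Baseline positive, Week 12 scan done (8 patterns): all 8 qualify.
- Baseline positive, Week 12 scan missed (8 patterns): the previous scan is the Baseline scan, so the 4 with a Week 48/WD scan qualify.

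In total 12 patterns qualify and 0 of them are Baseline-negative. The Baseline row for any lesion in spine or SIJ is therefore 100%. The separate SIJ, spine and regional rows are not forced to 100%.

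**2. Per-subject means and regional percentages.** Let p be the share of scanned subjects who are PET-negative at Baseline. Negatives have 0 lesions everywhere, so a mean or percentage over all scanned subjects equals (1-p) times its value among positives. The PET-PPS shows the value among positives, which is too high by 1/(1-p). This takes lesion load among positives to be unrelated to whether a follow-up scan was obtained.

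| Assumed p | True % with any lesion | Printed | Factor 1/(1-p) |
|---|---|---|---|
| 0 | 100 | 100 | 1.00 |
| 10% | 90 | 100 | 1.11 |
| 20% | 80 | 100 | 1.25 |
| 30% | 70 | 100 | 1.43 |
| 40% | 60 | 100 | 1.67 |

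**3. Totals.** Take 25 scanned subjects, p = 20% and 4 lesions per positive subject (both assumed), with every positive subject followed up. The total is 20 x 4 = 80 lesions in either set. The mean is 80/25 = 3.2 over all scanned subjects and 80/20 = 4.0 in the PET-PPS. The mean moves and the total does not. If some positive subjects have no follow-up scan, the PET-PPS total can only be lower.

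**4. Within-arm change, illustration only.** Suppose that lesion counts at each read are Poisson given a subject-specific mean, and that these means follow an exponential distribution with mean m (a gamma distribution with shape 1). Then p = 1/(1+m). Among subjects with at least one lesion at the first read:

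- expected first count = 1+m;
- expected second count with no true change = (1+m)[1 - 1/(1+m)^2];
- relative fall = 1/(1+m)^2 = p^2.

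For m = 2 the counts are 3.00 and 2.67, a fall of 11%. For p from 10% to 40% the fall is 1% to 16%. Nothing in the documents supports this model over another. Independent variation between reads also fits poorly with location-specific lesions that are read twice and adjudicated.

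**The case against.** The strongest reply is that the PET variable is change in bone formation, not Baseline prevalence, and that one fixed set across visits is a legitimate choice for showing change. The substudy is exploratory, with no formal power calculation and no formal modelling. The analysis set is named and defined, and the scan condition stands in the same SAP section as the summaries. Most of this is fair. It limits the importance of the point without removing it, because the plan also chooses to tabulate Baseline presence and lesions per subject, and on this set those rows cannot do their job.

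A second reply is that Baseline positivity can be recovered elsewhere. SAP 6.3 summarises Baseline SUVauc, and each subject's maximum SUVauc, for substudy subjects in the Safety Set. Volumes of interest are drawn only where lesions were identified, and SAP 3.1 prints n for continuous variables. The n for maximum SUVauc set against the substudy N therefore approximates the share positive, apart from missing quantification. This stands as a partial answer. It needs a calculation that the reader is not told to make, and it gives no lesion counts. No planned table states Baseline prevalence directly.

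A reader might infer that PET-negative subjects vanish from every table. They do not: the Safety Set substudy tables for demographics (SAP 6.2), Baseline characteristics (6.3), exposure (11.1) and adverse events (11.2) carry no PET condition. They are missing from the lesion summaries of SAP 8.3.6.2, where their reads are only listed.

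**Conclusion.** The point holds for the Baseline description. The any-lesion row at Baseline is 100% in both arms by construction. Baseline lesions per subject and regional percentages are overstated by about 1/(1-p): 1.11 to 1.67 for an assumed p of 10% to 40%, and not at all if every scanned subject is positive.

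Two assumptions carry this. First, the read that triggers the next scan agrees with the final read. The documents do not say whether a site read or the adjudicated read is the trigger, so a rare exception is possible. Second, for the size of the factor, positives with and without a follow-up scan have similar lesion loads.

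Three stronger conclusions might be inferred and are not supported:

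- **Inflated totals.** Total lesion counts and the total-lesion bar charts are sums, and the excluded negatives add zero.
- **A biased comparison of arms.** Selection uses the pre-treatment scan and the same rule in both arms, so it does not by itself bias the comparison.
- **A large spurious fall in lesions.** Some fall within each arm is expected from selection on a positive first read, but its size is unknown. In the illustration above, a fall of 25% would need p = 50%.

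The documents contain no table shells, so whether the tables would carry a label that discloses the selection cannot be judged. For an exploratory substudy this should be corrected, mainly because the correction is almost free.

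**What to change.** In SAP 3.5.8 and 8.3.6.2:

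1. Present the Baseline summaries of lesion presence and lesions per subject for all dosed substudy subjects with an evaluable Baseline PET-CT scan, counting PET-negative subjects as 0 lesions. Keep PET-MRI separate, because SAP 8.3.6.2 does not allow it to be aggregated with PET-CT in the summaries.
2. Keep the PET-PPS for the by-visit change summaries, and label these tables and figures as conditional on PET-positivity at Baseline.

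The cost is SAP wording and one extra denominator. Baseline reads are already made and listed for all substudy subjects with a scan, so no new scans or data are needed. SAP 1 provides for amendment before database lock. The relabelling discloses the selection behind the within-arm changes but does not remove it, since that selection comes from the scan schedule and not from the analysis set.

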15.2 General statistical considerations

Statistical evaluation will be performed by PAREXEL and supervised by the Exploratory Statistics and Global Statistical Sciences Departments of UCB.

All analyses will be performed using SAS® Version 9.2 or later (SAS Institute, Cary, NC, USA) or R Version 2.10.1 (R Development Core Team) or later, or OpenBUGS Version 3.0.6 or later.

Descriptive statistics will be used to provide an overview of the Baseline, efficacy and safety results. For categorical parameters, the number and percentage of subjects in each category will be presented by treatment group. The denominator for the percentages will be based on the number of subjects appropriate for the purpose of analysis. Unless otherwise noted, all percentages will be expressed to 1 decimal place. For continuous parameters, descriptive statistics will include n, mean, standard deviation (SD), median, minimum, and maximum. Two-

sided 95% confidence intervals, geometric means, and coefficient of variation (CV) will be presented for selected variables as appropriate.

Baseline for each assessment is defined as either the value obtained at Baseline (Visit 2) or the last available value obtained prior to treatment administration at the Screening Visit (Visit 1) (details to be specified in the SAP).

Formal statistical testing will be conducted for this study for the primary efficacy variable. Other efficacy variables will be summarized descriptively by treatment group. Additional exploratory analyses will be conducted as deemed appropriate.

